We will further present the proportion of participants reporting LNS sharing at the two time points, stratified by intervention group (table 6). Hypothesis 6 (on a difference in sharing between the study groups) will be tested with the same logistic mixed model as hypothesis 5. We will calculate difference in odds ratios of sharing at the two time points separately between 10g or 20g and 40g LNS groups. The null hypothesis of no differences between 10g or 20g and 40g LNS groups will be rejected if P<0.05.

Deviation from the recommended feeding mode

At both time points, we will calculate the proportion of participants who report deviation from the recommended feeding mode (Table 4). The formula to be used in the calculation of the proportion of deviating participants will be the following:

• number of guardians reporting that they gave the LNS supplement in some other mode than mixed with food (answer alternatives 1,2,3)/ total number of guardians providing data on this question * 100%.

For hypothesis testing (hypothesis 7 on a change in deviations from the recommendation over time) we will create a logistic regression model with deviation from the recommendation as a dependent variable and visit as an independent variable (intervention groups combined). With this model we will test the null hypothesis of no difference in deviation from recommended feeding mode between two time points and the null hypothesis will be rejected if P<0.05. Results of this test will be shown in the text. Next we will test the change in sharing over time by intervention group. We will create a mixed model with random intercept and random slope for time and interaction terms between groups and time of measurement. We will reject the null hypothesis of no change in deviation from the recommended feeding mode over time if P<0.05 (Table 5).

Exploratory analysis

We will include in table 4 data on the mean number of feedings on the preceding day, and the proportion of guardians reporting that feeding LNS was difficult. For these data, we will not perform any statistical tests on possible differences between the values by study group or time point.

Observations

In the text, we will count the proportion of participants who were observed consuming LNS and tabulate it by LNS intervention group. And for those who were seen to receive LNS, we will count the mean number of LNS servings given per day and tabulate that by LNS Intervention.

13. Design of figures and tables

The below figures and tables will be prepared based on the analysis:

Figure 1: Box-whisker plot of adherence percentage among participants receiving 10g, 20g, 40g LNS supplementation per day.

* mean and median for LNS-10g, LNS-20g and LNS-40g are, xxx, xxx, respectively.

Figure 2: The mean reported weekly adherence percentage among participants receiving 10g, 20g, 40g LNS supplementation per day.

Characteristic	LNS-10	LNS-20	LNS-40	P-value (test
	group	group	group	chi-square or
				anova/Kruskal-
				Wallis)
Child				
Number of participants	XXX	XXX	XXX	
Age, months, mean (SD)	xx (xx)	xx (xx)	xx (xx)	0.xxx
Length for age, adjusted for sex, mean (SD)	xx (xx)	xx (xx)	xx (xx)	0.xxx
Weight for height, adjusted for sex, mean (SD)	xx (xx)	xx (xx)	xx (xx)	0.xxx
Proportion of girls	xx %	xx %	xx %	0.xxx
Prevalence of moderate and severe stunting at 6	xx %	xx %	xx %	0.xxx
months of age				
Mother				
Age years, mean (SD)	xx (xx)	xx (xx)	xx (xx)	0.xxx
Schooling years, mean (SD)	xx (xx)	xx (xx)	xx (xx)	0.xxx
Proportion of married	xx %	XX %	xx %	0.xxx
Proportion of women with only one child	xx %	XX %	xx %	0.xxx
Household				
Household asset index, mean (SD)	xx (xx)	xx (xx)	xx (xx)	0.xxx
Number of u-5 children in family, mean (SD)	xx (xx)	xx (xx)	xx (xx)	0.xxx
Head of household is respondent's husband	xx %	XX %	xx %	0.xxx
Proportion enrolled from Mangochi	XX	XX	XX	0.xxx

Table 1: Participant and household characteristics at enrollment, by study group.

	Model:			
	$\hat{y}_{i} = b_{0} + b_{1}D_{i} + b_{2}S_{i} + b_{3}(D_{i} \times S_{i})$			
Variable	Coefficient	90 % CI	P-value	
Constant (b ₀)	XX.XX	xx.xx to xx.xx	X.XXX	
Difference in the mean adherence	XX.XX	xx.xx to xx.xx	X.XXX	
percentage between participants				
receiving 20 g / day milk-free LNS				
and participants receiving 20 g / day				
milk-containing LNS (b ₂)				
Difference in the mean adherence	XX.XX	xx.xx to xx.xx	X.XXX	
percentage between participants				
receiving 40 g / day milk-free LNS				
and participants receiving 40 g / day				
milk-containing LNS $(b_2 + b_3)$				

Table 2 The association between the milk content in LNS and the guardian reported LNS adherence percentage, by the dose of LNS: results from a regression analysis.

Table 3: The association between LNS dose, selected participant and household characteristics and LNS adherence percentage.

		Unadjusted analysis		Adjusted analysis	
Predictor variable	n	Coefficient (95% CI)	Р-	Coefficie	P-value
			value	nt (95%	
				CI)	
Daily LNS dose					
10 g (Constant)	XXX	xx.x (x.x to x.x)	0.xxx		
20 g	XXX	x.x (x.x to x.x)	0.xxx		
40 g	XXX	x.x (x.x to x.x)	0.xxx		
Constant		xx.x (x.x to x.x)	0.xxx		
Time in study, weeks	XXX	x.x (x.x to x.x)	0.xxx		
Child sex					
Boy (Constant)	XXX	xx.x (x.x to x.x)	0.xxx		
Girl	XXX	x.x (x.x to x.x)	0.xxx		
Constant		xx.x (x.x to x.x)	0.xxx		
Child LAZ at enrolment,	XXX	x.x (x.x to x.x)	0.xxx		
Z-score					
Constant		xx.x (x.x to x.x)	0.xxx		
Child WHZ at	XXX	x.x (x.x to x.x)	0.xxx		
enrolment, Z-score					
Constant		xx.x (x.x to x.x)	0.xxx		
Maternal age, years	XXX	x.x (x.x to x.x)	0.xxx		
Number of children					
1 (Constant)	XXX	xx.x (x.x to x.x)	0.xxx		
2	XXX	x.x (x.x to x.x)	0.xxx		
3+	XXX	x.x (x.x to x.x)	0.xxx		
Constant		xx.x (x.x to x.x)	0.xxx		
Maternal education,	XXX	x.x ($x.x$ to $x.x$)	0.xxx		
years					
Maternal ability to read					
None (Constant)	XXX	xx.x (x.x to x.x)	0.xxx		
With difficulty	XXX	x.x (x.x to x.x)	0.xxx		
Fluently	XXX	x.x (x.x to x.x)	0.xxx		
Maternal ability to write					
None (Constant)	XXX	xx.x (x.x to x.x)	0.xxx		
With difficulty	XXX	x.x ($x.x$ to $x.x$)	0.xxx		

Fluently	XXX	x.x ($x.x$ to $x.x$)	0.xxx	
Maternal marital status				
Married (Constant)	XXX	xx.x (x.x to x.x)	0.xxx	
Single	XXX	x.x ($x.x$ to $x.x$)	0.xxx	
Other	XXX	x.x (x.x to x.x)	0.xxx	
Maternal tribe				
Chewa (Constant)	XXX	xx.x (x.x to x.x)	0.xxx	
Yao	XXX	x.x (x.x to x.x)	0.xxx	
Other	XXX	x.x ($x.x$ to $x.x$)	0.xxx	
Head of household				
Head of household is	XXX	xx.x (x.x to x.x)	0.xxx	
respondent's				
husband (Constant)				
Head of household is	XXX	x.x ($x.x$ to $x.x$)	0.xxx	
not respondent's				
husband				
Constant		xx.x (x.x to x.x)	0.xxx	
Number of children	XXX	x.x ($x.x$ to $x.x$)	0.xxx	
under-5				
Constant		xx.x (x.x to x.x)	0.xxx	
Household asset index,	XXX	x.x (x.x to x.x)	0.xxx	
index-score				
Constant		xx.x (x.x to x.x)	0.xxx	
Household food security,	XXX	x.x (x.x to x.x)	0.xxx	
index-score				
Site of residence				
Mangochi (Constant)	XXX	xx.x (x.x to x.x)	0.xxx	
Other	XXX	x.x (x.x to x.x)	0.xxx	

	Duration of LNS provision		
	6 months	12 months	
Mean (SD) weekly adherence percentage	xx.x (xx.x)	xx.x (xx.x)	
(on 7 days in the preceding week)			
Proportion of guardians reporting deviation	xxx/xxx	xxx/xxx	
from the recommendation of daily LNS	(xx.x%)	(xx.x%)	
provision during the preceding week			
Proportion of guardians reporting LNS	xxx/xxx	xxx/xxx	
sharing during the preceding week	(xx.x%)	(xx.x%)	
Proportion of guardians reporting deviation	xxx/xxx	xxx/xxx	
from the recommended feeding mode (mix	(xx.x%)	(xx.x%)	
with food) during the preceding week			
Mean (SD) number of LNS feedings on the	xx.x (xx.x)	xx.x (xx.x)	
preceding day			
Proportion of guardians reporting that	xxx/xxx	xxx/xxx	
feeding LNS was difficult	(xx.x%)	(xx.x%)	

Table 4: Participant adherence to feeding recommendations and experience from LNS use; results from KAP interviews at two time points.

	Model:			
	$\hat{\mathbf{y}}_{i} = \mathbf{b}_{0} + \mathbf{b}_{1} \operatorname{time}_{ij} + \mathbf{b}_{2} \operatorname{LNS10g}_{i} + \mathbf{b}_{3} \operatorname{LNS20g}_{i} + \mathbf{b}_{4} (\operatorname{LNS10g}_{i})$			
	×	$time_{ij}$ + b_5 (LNS20 $g_i \times time_{ij}$	e _{ij})	
Outcome variable	Daily LNS dose	OR (95% CI)	P-value	
Change in odds ratio over	10 g (b ₄ x time)	xx.x (x.x to x.x)	0.xxx	
time for guardians reporting	20 g (b₅ x time)	xx.x (x.x to x.x)	0.xxx	
deviation from the	$40 \text{ g} (b_1 \text{ x time})$	xx.x (x.x to x.x)	0.xxx	
recommendation of daily				
LNS provision during the				
preceding week				
Change in odds ratio over	10 g (b ₄ x time)	xx.x (x.x to x.x)	0.xxx	
time for guardians reporting	20 g (b₅ x time)	xx.x (x.x to x.x)	0.xxx	
LNS sharing during the	$40 \text{ g} (b_1 \text{ x time})$	xx.x (x.x to x.x)	0.xxx	
preceding week				
Change in odds ratio over	10 g (b ₄ x time)	xx.x (x.x to x.x)	0.xxx	
time for guardians reporting	20 g (b₅ x time)	xx.x (x.x to x.x)	0.xxx	
deviation from the	$40 \text{ g} (b_1 \text{ x time})$	xx.x (x.x to x.x)	0.xxx	
recommended feeding mode				
(mix with food) during the				
preceding week				

Table 5. The association between daily dose of supplemented LNS and change in adherences to the recommendations on LNS use between two time points. Results from a logistic mixed model

	Daily LNS dose			
	10g	20g	40g	
Proportion of guardians reporting LNS	xxx/xxx	xxx/xxx	xxx/xxx	
sharing during the preceding week, at 6	(xx.x%)	(xx.x%)	(xx.x%)	
months				
Difference in OR between 10g or 20g dose	xx.x (xx.x to	xx.x (xx.x to	Ref.	
and 40g dose	xx.x)	xx.x)		
P-value	XXX.X	XXX.X		
Proportion of guardians reporting LNS	xxx/xxx	xxx/xxx	xxx/xxx	
sharing during the preceding week, at 12	(xx.x%)	(xx.x%)	(xx.x%)	
months				
Difference in OR between 10g or 20g dose	xx.x (xx.x to	xx.x (xx.x to	Ref.	
and 40g dose	xx.x)	xx.x)		
P-value	XXX.X	XXX.X		

Table 6: The association between daily dose of supplemented LNS, time in study, and supplement sharing. Results from a logistic mixed model presented in Table 5.

Although nutritional supplementation is one of the recommended ways to combat child undernutrition, emerging evidence suggests that the supplements may be harmful in some instances. While a beneficial effect of nutrient supplementation on morbidity has been shown in some studies (Sharieff et al. 2006), big studies have shown that supplementation with multiple micronutrient powders or iron tablets may be associated with increased risk of common childhood infections (Sazawal et al, 2006, Soofi et al, 2013). Lipid-based nutrient supplement (LNS) is a product being tested for its potential in prevention of under nutrition and improving child growth outcomes in a randomised controlled trial in a rural Malawian population. It may be important to provide evidence of safety of LNS provision in settings where childhood infections are common. Previous studies on LNS have reported that the product appears to be safe but the evidence is still not conclusive. Such studies had either relatively short duration, i.e. 6 months or less, or did not have sufficient power because of small sample size (Dewey & Baldiviez, 2012). This study aims at assessing the safety of LNS when provided to healthy infants and young children for a period of 12 months. We will also explore any beneficial effects of LNS provision on morbidity, as an additional outcome.

3 Study objective

The main aim of this study is to assess the safety outcomes in children participating in the iLiNS-DOSE study in rural communities in Malawi. The outcomes are categorised as serious adverse events (SAE), non-scheduled visits, self-reported morbidity symptoms and self-reported disease episodes.

3.1 Specific objectives

The specific objective of the study is to compare the following outcomes between the study groups after 12 months of intervention:

- i. Risk of SAEs (hospitalizations and deaths).
- ii. Incidence of non-scheduled visits made by the participants to health facilities due to malaria or any other illnesses.
- iii. Longitudinal prevalence of self-reported common childhood morbidity symptoms.
- iv. Incidence of common childhood infectious disease episodes.

4 Hypotheses to be tested

- a) Risk of SAEs (deaths or hospitalizations) is not markedly higher in children receiving LNS than in children who receive no dietary intervention.
- b) Incidence of non-scheduled visits made to health facilities due to malaria or any other illnesses is not markedly higher in children receiving LNS than in children who receive no dietary intervention.
- c) Longitudinal prevalences of self-reported morbidity symptoms are not markedly higher in children who receive LNS than in children who receive no dietary intervention at the same age.
- d) Incidences of self-reported episodes of common childhood infectious disease episodes (malaria, acute respiratory illnesses and gastroenteritis) are not markedly higher in children who receive LNS than in children who receive no dietary intervention at the same age.

5 Definitions of end-points

Serious adverse events (SAE): Defined according to United States Department of Health and Human Services Office for Human Research Protections (www.fda.gov). The data will be extracted from form 29, Q 3.2.

Non-scheduled visits: Non-scheduled visits are a composite of morbidity, access to health care and health seeking behaviour. The total number of visits to a health facility made by the participant during the study period, as well as clinical diagnoses made by health workers at the

non-scheduled visits will be analysed. *The data will be extracted from form 26 (total) and form 26, Q 4.1.*

Self-reported symptoms of any illness for each day were collected at a weekly home visit. These data will be extracted from form 18 where the following symptoms were recorded: *low appetite* $(Q\ 2.6)$, *diarrhoea* $(Q\ 2.7)$, *bloody stools* $(Q\ 2.8)$, *mucoid stools* $(Q\ 2.8)$, *vomiting* $(Q\ 2.9)$, *fever* $(Q\ 2.10)$, *cough* $(Q\ 2.11)$, *rapid breathing* $(Q\ 2.12)$, *difficult breathing* $(Q\ 2.13)$ and nasal discharge $(Q\ 2.14)$.

Diagnoses of malaria, gastroenteritis and acute respiratory infections (ARI) were derived from presence of a combination of self-reported symptoms on one or more days. To ensure that the diagnoses are mutually exclusive, a diagnosis algorithm was created whereby any diarrhea episode (\geq 3 loose stools in 24 hours) was categorized as gastroenteritis in the presence or absence of other symptoms. If diarrhea was absent but there was presence of any respiratory symptoms (cough, rapid or difficult breathing and nasal discharge) with or without fever, a diagnosis of ARI was made. Fever episodes in the absence of diarrhea and respiratory symptoms, with or without other symptoms, were categorized as malaria. The rest of the symptoms in the absence of diarrhea, respiratory symptoms and fever were categorized as "others". For all diseases, an episode was defined as the period starting from the day the child had symptoms which was then followed by at least 2 symptom-free days.

6 Basis of analysis: Intention to treat and per protocol analysis

A total of 1932 six-month-old children were randomized into five intervention groups to receive the following daily doses: 10 g milk-LNS, 20 g milk-LNS, 20 g non-milk-LNS, 40 g milk-LNS, 40 g non-milk-LNS and a control (no dietary intervention) group. In the first analysis we will compare the outcomes among all six groups, with the aim of testing the difference between the milk and milk-free groups. We will test the hypothesis of no difference in the longitudinal prevalence of any illness using least squares regression. The regression model will be estimated as follows:

$$\hat{y}_i = b_0 + b_1 D_i + b_2 S_i + b_3 (D_i \times S_i)$$

where D = 0 or 1 for the 20g and 40g group, respectively, and S = 0 or 1 for the milk and milk-free LNS group, respectively. Participants who received 10g / day milk-LNS and participants who received no dietary intervention will be excluded in this model. Coefficient b_2 will indicate whether the 20g milk-LNS group differs from 20g milk-free LNS group and linear combination of coefficients b_2+b_3 (Stata's *lincom* command) will tell us whether the 40g milk-LNS group differs from 40g no-milk-LNS group. If P<0.05 for coefficient b_2 or b_2+b_3 we will reject the null hypothesis of no differences between groups and use separate groups for 20g and 40g milk and milk-free LNS groups in the subsequent analyses. If P>0.05 for coefficient b_2 or b_2+b_3 we will combine milk and milk-free LNS groups in the subsequent analyses.

Another analysis will be done to compare all the LNS groups combined against the control (no dietary intervention) group.

These analyses will primarily be based on principle of *modified* intention-to-treat. The modification is due to six participants who were accidentally allocated to a group other than the one to which they were actually randomized. For each participant, the randomization code was pre-packed and sealed in an individual envelope that was opened and used for group allocation at enrolment. For these 6 individuals, the randomizer made a recording error, i.e. s/he noted down in a data collection form an incorrect group code or wrote the code with unclear handwriting. The incorrect code was later transcribed into the computer software that was used to plan participant visits and allocate interventions. These six participants were told to belong to the erroneously recorded intervention group and they received that intervention throughout the trial – hence they will also be analyzed in that group (rather than the one written on the randomization slip). All randomized participants are eligible to be included in the analysis of that outcome.

Besides the intention to treat, per protocol analysis will be done by restricting the analysis to those consuming the supplements for at least 70% of the intervention period.

7 Time points for analyses

All the above analyses will cover the period from enrolment (when the participants are 6 months old) to the end of the intervention (when the participants are 18 months old).

8 Calculation of end-points, presentation of study findings and comparison between groups

8.1 Participant flow

All screened and enrolled infants and the success of the follow up will be described in a flow chart according to CONSORT guidelines (Figure 1). For additional information the drop-out rate between groups will be compared with Fisher's exact test but will not be included in Figure 1.

8.2 Baseline characteristics

Participant characteristics at enrolment will be tabulated by treatment arms (Table 1). Hypothesis testing will be performed for baseline characteristics to give additional information. Methods used for hypothesis testing are also indicated in Table 1, but p-values will not be presented in the final manuscript. Baseline characteristics of refusals and drop-outs will be compared to those who completed the study. P-values for these tests will be shown in the text.

8.3 Risk of serious adverse events

Risk of any SAE, hospitalization and death will be calculated as number of participants having any SAE or hospitalization or death / the total number of participants in each group (Table 2). These events are counted once for each participant, as opposed to total SAEs which was a repeated event in some participants. Risk ratio (95% CI) will be calculated for each intervention group using the control group as reference. Cumulative incidence curve for deaths for each group will be shown in Figure 2.

8.4 Incidence of non-scheduled visits

The total number of non-scheduled visits will be tabulated by intervention group. The incidence of non-scheduled visits will be calculated as the number of non-scheduled visits / the total days of follow up in each group (Table 3). Incidence rate ratio (95% CI) will be calculated for each intervention group using the control group as reference.

8.5 Longitudinal prevalences of self-reported common childhood morbidity symptoms

Longitudinal prevalence is defined as the proportion of days with the symptom in the study period. This will be calculated as total days of each reported morbidity symptom / total number

of days of follow up for each participant in each group to obtain group means. Geometric means ratio (95% CI) will be used to estimate and compare the mean longitudinal prevalences among the intervention and control groups using the control group as the reference. Results will presented by intervention group (Table 4).

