8.6 Incidences of common childhood infectious disease episodes

Incidence of episodes for each disease (number of episodes per child / total days of follow up per child) will be presented by intervention group. Incidence rate ratios (95% CI) will be calculated for each intervention group using the control group as the reference. Results will presented by intervention group (Table 5).

9 Hypothesis testing and statistical modelling

Risk of serious adverse events will be analysed using generalised linear modelling (log-binomial family). The Cox regression will be used in the analysis of mortality outcome. Differences in longitudinal prevalences of self-reported symptoms will be analysed and tested using least squares regression. Incidences of non-scheduled visits and morbidity episodes will be analysed using negative binomial regression.

The following is the list of the end-points and the types of modelling to be used for each endpoint:

End-p	oint	Statistical modelling		
i.	Risk of SAE	Log-binomial regression		
ii.	Longitudinal prevalence	Least squares regression		
iii.	Incidence of non-scheduled visits	Negative binomial regression		
iv.	Incidence of disease episodes	Negative binomial regression		

A set non-inferiority margin of 20% will used to test the hypotheses of no marked increase in the risk of SAEs, incidences of non-scheduled visits and morbidity episodes and prevalences of self-reported morbidity symptoms due to the intervention. An increased risk of >20% (risk ratio/incidence rate ratio >1.20) suggests a harmful effect associated with the intervention. The non-inferiority margin of 20% or an incidence difference of 20% has been used in previous

studies on nutritional supplementation and morbidity (Lemaire et al, 2011; Sazawal et al, 2006; Soofi et al, 2013).

The findings of the analysis will lead to one of the following four possible conclusions:

- i. If the upper bound of the 95% CI for the risk ratio/incidence rate ratio is <1.20, a conclusion of non-inferiority will be made.
- ii. If the lower bound of the 95% CI for the risk ratio/incidence rate ratio is >1.20, a conclusion of inferiority will be made.
- iii. If the upper bound of the 95% CI for the risk ratio/incidence rate ratio is <1.00, superiority will be confirmed (suggesting a beneficial effect).

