10.2 Preparing morbidity data for analysis

Using the weekly morbidity form (Form 18, table) morbidity variables were split to create a new dataset for each morbidity symptom. I created new variables for total days with symptoms and total follow up days in each dataset which were used to calculate prevalence of each morbidity symptom per child. Mean longitudinal prevalences for each group were derived from the individual prevalences. I created morbidity episodes from a combination of symptoms by merging the datasets of self-reported symptoms. Incidences in a group were calculated as the sum of events/episodes across individuals divided by sum of follow-up times across individuals. Preparation of these data was done using STATA and detailed steps taken in preparation of these data were recorded in a STATA do file

10.3 Confidence intervals

The confidence intervals at 95% level (95% CI) will be provided for all the outcomes. I will use log-binomial regression to derive the confidence intervals for SAE risk ratio, geometric means ratio to derive the confidence intervals for mean longitudinal prevalence and negative binomial regression to derive the confidence intervals for incidence of nonscheduled visit and self-reported disease episodes.

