10.5 Covariate adjustment

The main analysis will be completed and shown in figures and tables without any covariate adjustment.

As a secondary analysis, generalised linear modelling (log-binomial family) will be used to model the possible predictors of SAEs. Least squares regression will be used to model the percentage of days with self-reported morbidity symptoms. Negative binomial regression will be used to model the predictors of non-scheduled visits and disease episodes. Fixed effects will be used to model for age (grouped in 2 age bands) and seasonal variation. All variables which show a statistically significant association with any of the outcomes (at p<0.05) will be included in the regression models. The covariates to be included in the models will be derived from the list below:

- a. Child length for age z-score, weight for age z-score and weight for length z-score at baseline
- b. Child sex
- c. Maternal education and marital status
- d. Proxy for hygiene/water quality
- e. Iron status at baseline
- f. Anaemia status at baseline
- g. Household food insecurity access (HFIA)
- h. Seasonality
- i. Age (divided into two bands: <12 months and >12 months)

11 References

Kathryn G. Dewey and Lacey M. Baldiviez. Safety of Universal Provision of Iron through Home Fortification of Complementary Foods in Malaria-Endemic Areas. *Adv. Nutr* 2012;**3**:555–559.

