	Incidence			Comparison between the groups			
				Incidence rate ratio (95%CI)			
Variable	Control	10g LNS	20g LNS	40g LNS	10g LNS vs	20g LNS vs	40g LNS vs
					control	control	control
Number of participants	XXX	XXX	XXX	XXX	-	-	-
Total follow up days	XXXXX	XXXXX	XXXXX	XXXXX	-	-	-
Non-scheduled visits	x.xx (xxxx)	x.xx (xxxx)	x.xx (xxxx)	x.xx (xxxx)	x.xx (xx to xx)	x.xx (xx to xx)	x.xx (xx to xx)
Gastroenteritis	x.xx (xxxx)	x.xx (xxxx)	x.xx (xxxx)	x.xx (xxxx)	x.xx (xx to xx)	x.xx (xx to xx)	x.xx (xx to xx)
Acute respiratory infections	x.xx (xxxx)	x.xx (xxxx)	x.xx (xxxx)	x.xx (xxxx)	x.xx (xx to xx)	x.xx (xx to xx)	x.xx (xx to xx)
Clinical malaria	x.xx (xxxx)	x.xx (xxxx)	x.xx (xxxx)	x.xx (xxxx)	x.xx (xx to xx)	x.xx (xx to xx)	x.xx (xx to xx)
Others	x.xx (xxxx)	x.xx (xxxx)	x.xx (xxxx)	x.xx (xxxx)	x.xx (xx to xx)	x.xx (xx to xx)	x.xx (xx to xx)

Incidence = number of events / total follow up days

Page 16 of 17

TABLE 4:

Longitudinal prevalence of self-reported common childhood morbidity symptoms

	Prevalence				Comparison between the groups Geometric means ratio (95%CI)			
Variable	Control	10g milk LNS	20g LNS	40g LNS	10g LNS v control	20g LNS v control	40g LNS vs control	
Total follow up days	xxxxx	XXXXX	XXXXX	XXXXX	-	-	-	
Any illness	XX.X%	xx.x%	XX.X%	xx.x%	x.xx (xx to xx)	x.xx (xx to xx)	x.xx (xx to xx)	
Fever	XX.X%	xx.x%	XX.X%	xx.x%	x.xx (xx to xx)	x.xx (xx to xx)	x.xx (xx to xx)	
Cough	XX.X%	xx.x%	XX.X%	xx.x%	x.xx (xx to xx)	x.xx (xx to xx)	x.xx (xx to xx)	
Vomiting	XX.X%	xx.x%	XX.X%	xx.x%	x.xx (xx to xx)	x.xx (xx to xx)	x.xx (xx to xx)	
Rapid breathing	xx.x%	xx.x%	xx.x%	xx.x%	x.xx (xx to xx)	x.xx (xx to xx)	x.xx (xx to xx)	
Difficult breathing	XX.X%	xx.x%	XX.X%	xx.x%	x.xx (xx to xx)	x.xx (xx to xx)	x.xx (xx to xx)	
Nasal discharge	XX.X%	xx.x%	xx.x%	xx.x%	x.xx (xx to xx)	x.xx (xx to xx)	x.xx (xx to xx)	
Diarrhoea	xx.x%	xx.x%	xx.x%	xx.x%	x.xx (xx to xx)	x.xx (xx to xx)	x.xx (xx to xx)	
Bloody stools	xx.x%	xx.x%	xx.x%	xx.x%	x.xx (xx to xx)	x.xx (xx to xx)	x.xx (xx to xx)	
Mucoid stools	xx.x%	xx.x%	xx.x%	xx.x%	x.xx (xx to xx)	x.xx (xx to xx)	x.xx (xx to xx)	

Longitudinal prevalence = number of days with symptom / total number of days of follow up

TABLE 5:

Incidence of self-reported disease episodes

	Incidence				Comparison between the groups			
					Incidence rate ratio (95%CI)			
Variable	Control	10g milk	20g LNS	40g LNS	10g LNS v	20g LNS v	40g LNS vs	
		LNS			control	control	control	
Total follow up days	XXXXX	XXXXX	XXXXX	XXXXX	-	-	-	

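### Appendix 08 compares symptom prevalences by a geometric means ratio without a rule for children with zero symptom days, so the ratio meant for the 1.20 safety margin cannot be computed as written

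*SAP*

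**What the plan says.** All places are in Appendix 08 of the SAP.

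- **Outcome.** Section 8.5: "Longitudinal prevalence is defined as the proportion of days with the symptom in the study period". It is calculated for each participant. The note under Table 4 repeats the formula: "Longitudinal prevalence = number of days with symptom / total number of days of follow up".
- **Effect measure.** Section 8.5: "Geometric means ratio (95% CI) will be used to estimate and compare the mean longitudinal prevalences among the intervention and control groups", with control as reference. Table 4 has a column for this ratio in every row, including bloody stools, mucoid stools, rapid breathing and difficult breathing.
- **Confidence interval.** Section 10.3 uses the "geometric means ratio to derive the confidence intervals for mean longitudinal prevalence".
- **Group summary.** Section 10.2: "Mean longitudinal prevalences for each group were derived from the individual prevalences". No log transformation is mentioned.
- **Test.** Section 9: "Differences in longitudinal prevalences of self-reported symptoms will be analysed and tested using least squares regression". The scale is not stated.
- **Secondary model.** Section 10.5: "Least squares regression will be used to model the percentage of days with self-reported morbidity symptoms".
- **Margin.** Section 9: "A set non-inferiority margin of 20% will used to test the hypotheses of no marked increase". The sentence goes on to list symptom prevalences among the outcomes covered. The decision rule that follows compares the 95% bounds with 1.20, but names only the risk ratio and the incidence rate ratio.

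Appendix 08 gives no exclusion, added constant or two-part analysis for zeros. Appendix 06 (footnote to section 2.1) recognises the same difficulty and states a replacement value, but only for willingness-to-pay.

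**The concern.** Section 4 of the appendix makes symptom prevalence one of four safety hypotheses, each asking whether LNS causes a marked increase. A geometric mean is exp(mean of log x), so one child at 0 sends it to 0 and leaves its log undefined. The ratio and its interval then do not exist unless the analyst decides what to do with the zeros.

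That decision is not neutral. Leaving the zeros out compares only children who had the symptom, a subset formed after randomisation, and ignores any rise in how many children are affected. Adding a constant keeps everyone, but the ratio then depends on the constant. Falling back on the least squares model in sections 9 and 10.5 avoids the log but changes the estimand to a difference, for which the appendix has no margin. At stake is whether a true increase in a symptom is declared non-inferior, inferior or inconclusive.

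**Working it through.** The SAP gives no power, sample size or prevalence figure for this outcome, so there is nothing to reproduce. The checks below use the plan's own definitions and decision rule.

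**Inputs from the SAP.** 1932 children in six groups, so 1932/6 = 322 per group if allocation is equal, and 644 in a pooled 20 g or 40 g group. Follow-up runs from 6 to 18 months of age, about 365 days. Non-inferiority requires an upper 95% bound below 1.20.

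**Assumed, because the SAP does not give them.** The share of children ever affected, and the days per affected child (log-normal, median 3 or 4 days for the less common symptoms, log-SD 0.8).

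**Step 1: will there be zeros?** If a fraction f of children never has the symptom, P(at least one zero among 322) = 1 − (1 − f)^322. For f = 0.5%, 1% and 5% this is 80%, 96% and over 99.9%.

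**Step 2: how far does the choice move the ratio?** Let shares p0 (control) and p1 (LNS) be affected, each affected child having d days, with c days added to every child. Follow-up days cancel, and

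GMR = exp{(p1 − p0) × ln[(d + c)/c]}.

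The true ratio of means is p1/p0. With p0 = 0.20, p1 = 0.30 and d = 3, it is 0.30/0.20 = 1.50. For c = 0.01, GMR = exp(0.10 × ln 301) = 1.770. For c = 3.65 (one percentage point of 365 days), GMR = exp(0.10 × ln 1.822) = 1.062. With zeros dropped, affected children are alike in both arms and GMR = 1.00.

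**Step 3: what does the decision rule do?** Simulation, 322 control and 644 LNS children, 1500 replicates, least squares on the log scale:

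| Handling of zeros | GMR, formula | GMR, simulated | Non-inferior | Inferior |
|---|---|---|---|---|
| Dropped | 1.00 | 1.000 | 39% | 0% |
| + 0.01 day | 1.770 | 1.768 | 0% | 60% |
| + 0.1 day | 1.410 | 1.411 | 0% | 33% |
| + 0.5 day | 1.215 | 1.220 | 1% | 4% |
| + 1 day | 1.149 | 1.155 | 12% | 0.1% |
| + 3.65 days | 1.062 | 1.070 | 100% | 0% |

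The simulated ratio of arithmetic means averaged 1.54, slightly above 1.50 because a ratio of sample means is skewed.

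**Step 4: other assumed frequencies.**
- 10% v 15% affected (true 1.50): GMR 1.33 at 0.01 day and 1.04 at 3.65 days, with non-inferiority concluded in 0.2% and 100% of trials. Dropping zeros gives 1.00 and 22%.
- 50% v 75% affected, median 4 days (true 1.50): dropping zeros gives 1.00 and non-inferiority in 72%. Adding 0.01 day gives 4.49, a large overstatement.
- 99% affected in both arms, median 40 v 60 days (simulated mean ratio 1.48): GMR 1.44 to 1.50 under every handling above, and non-inferiority is never concluded.

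**Step 5: sensitivity of the dropped-zeros result.** With 300 children per arm and geometrically distributed days among the affected, 20% v 30% gives non-inferiority in about 33% of trials at a mean of 3 days. It falls to about 16-17% at a mean of 20 days and rises to about 47% at 2 days.

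**Step 6: the raw-scale alternative.** A difference of one percentage point is a ratio of 3/2 = 1.50 if control prevalence is 2%, and 21/20 = 1.05 if it is 20% (illustrative values). A least squares difference therefore cannot be judged against 1.20 unless it is converted, and no conversion is given.

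**The case against.** The strongest reply is that this is one missing detail in one of four outcome types. Much of the same symptom information also feeds the disease episodes in section 5: diarrhoea to gastroenteritis, respiratory symptoms to ARI, fever to malaria. Those episodes, like the non-scheduled visits, are analysed by negative binomial regression over all children, where a zero is valid, so a rise in affected children would tend to show there against the same margin. Serious adverse events are untouched. This stands and limits the exposure, mainly to the rarer rows of Table 4. It does not make those rows computable, and the appendix tests them as a separate hypothesis.

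Three stronger readings are tempting, and the SAP does not support them:

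- A reader might infer that the method always favours a finding of no harm. It does not: dropping zeros or adding a large constant hides harm, while a very small constant overstates it.
- A reader might infer that children with zeros will be dropped, since statistical software treats log(0) as missing. The appendix never says so, and section 10.2 builds group means from the individual prevalences. Dropping is one possible implementation.
- A reader might extend the point to the least squares test on any illness that decides whether milk and milk-free groups are pooled (section 6). That test names no log or geometric mean, and its outcome probably has few zeros. It is not part of this point.

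It is also fair that the decision rule uses the upper bound, so the 20% v 30% example with zeros dropped is more often inconclusive than falsely reassuring.

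**Conclusion.** The point holds in this form: the effect measure and interval in sections 8.5 and 10.3 and Table 4 are undefined once any child has zero symptom days. No zero rule is given, and the models in sections 9 and 10.5 do not supply a ratio on the raw scale. For symptoms that many children never have, plausibly bloody or mucoid stools and rapid or difficult breathing, the conclusion depends on a choice the plan leaves open. At an assumed 20% v 30% ever affected and a true ratio of 1.50, the reported ratio runs from about 1.0 to 1.8. The chance of concluding non-inferiority is roughly 35-40% with zeros dropped, and anywhere from 0% to 100% across the added constants.

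The undefined ratio follows from the definitions alone. Its size rests on assumed frequencies and days per affected child, because the SAP reports neither. For near-universal symptoms the effect is small.

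**What to change.** Replace the geometric means ratio with the ratio of mean symptom days per follow-up day. Estimate it by negative binomial regression of symptom days on group, with log follow-up days as offset and robust standard errors, because symptom days cluster within episodes. Children with no symptom days then contribute without any constant.

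Align the text with it: the effect measure in section 8.5, the model list in section 9, the interval in section 10.3, the secondary model in section 10.5, and the column heading in Table 4. Show the group prevalences in Table 4 on the same basis as the ratio. Add this ratio by name to the 1.20 decision rule in section 9. Intervals for rare symptoms will be wide, and the rule already provides an inconclusive outcome for that case.

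A two-part analysis or a stated zero rule would also close the gap, but a rule based on a constant would keep the dependence shown above. The cost is SAP wording only. The appendix already uses negative binomial regression for visits and episodes, and no new data are needed.
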